| HIPAA | Health Insurance Portability and Accountability Act |
| IAD | Incontinence Associated Dermatitis |
| ICF | Informed Consent Form |
| ICH | International Conference on Harmonization |
| IRB/EC | Institutional or Independent Review Board/Ethics Committee |
| MDCG | Medical Device Coordination Group |
| MDR | Medical Device Regulation |
| NDA | Non-disclosure Agreement |
| NSR | Non-significant Risk |
| OAB | Overactive Bladder Syndrome |
| PI | Principal Investigator |
| PUCS | PureWick [™] Urine Collection System |
| PW | PureWick [™] Female External Catheter |
| N-QOL | Nocturia Quality of Life |
| QOL | Quality of Life |
| RCT | Randomized Control Trial |
| RMV | Routine Monitoring Visit |
| SADE | Serious Adverse Device Effect |
| SAE | Serious Adverse Event |
| SD | Standard Deviation |
| SIV | Site Initiation Visit |
| SFTP | Secure File Transfer Protocol |

| SoA | Schedule of Activities |
|-------|--|
| SOP | Standard Operating Procedure |
| TMF | Trial Master File |
| UADE | Unexpected Adverse Device Effect |
| UI | Urinary Incontinence |
| U.S. | United States |
| USADE | Unexpected Serious Adverse Device Effect |

| Protocol Title | A Comparative Crossover Study on the Safety, Efficacy, and Patient Quality of Life Comparing PureWick [™] System with an Established Comparator Overnight in the Home Setting for Incontinence. | | |
|--------------------------|---|---|--|
| Short Title | PureWick [™] At-Home Pilot Study | | |
| Rationale | The study will collect clinical and quality of life data from patients requiring urine output management overnight in the home setting, which will aid reimbursement in France and the United States (U.S.). This pilot will inform the sample size and the frequency of nursing visits for the future randomized control trial. | | |
| Objectives and Endpoints | Objective(s) | Endpoint(s) | |
| | Primary To compare efficacy and safety of PureWick [™] System and Hollister® Female Urinary Pouch External Collection Device | Primary Efficacy – Daily capture rate via bed pad weights and captured volume. Safety – Daily skin irritation score using the Draize Scale. | |

| | Secondary | Secondary |
|---------------------|---|---|
| | To assess impact of PureWick[™] System and Hollister[®] Female Urinary Pouch External Collection Device on Nocturnal Incontinence related Quality of Life and Sleep | Nocturia Quality of Life (N-QOL) score collected at baseline and every 2 weeks during treatment PROMIS Sleep Disturbance score at baseline and every 7th day during treatment. |
| | Tolerability – To assess the tolerance of PureWick[™] System and Hollister[®] Female Urinary Pouch External Collection Device over the expected duration of use | Tolerability – Number of days of actual use of both devices & Discontinuation rate attributed to the device's inconvenience or discomfort. |
| | To assess participant comfort and ease of use of PureWick[™] System and Hollister[®] Female Urinary Pouch External Collection Device | • Overall comfort and ease of use scores on a 5-point Likert scale (brief questionnaire) collected at the end of each treatment phase. |
| | To assess participant preference between the PureWick[™] System and Hollister® Female Urinary Pouch External Collection Device after study completion | • Overall preference via end of study participant preference survey administered at study completion. |
| Design and Overview | In this prospective, open-label, crossover trial, approximately 30 women with Nocturnal Urinary | |

| Date. 10 Apr 2024 | |
|------------------------|---|
| | Incontinence requiring the use of diapers in bed will be 1:1 randomized to a treatment sequence using two devices (PureWick TM System and Hollister® Female Urinary Pouch External Collection Device) and followed for approximately 10 weeks through 2 treatment phases. For purposes of this study, the PureWick TM System will be referenced to include the PureWick TM Female External Catheter used in conjunction with the PureWick TM Urine Collection System, including the tubing and the canister. |
| | At the start of the study, participants will be consented and screened against inclusion/exclusion criteria. All subjects that have met all eligibility criteria will be assigned a treatment order. Participants will view the training video for the applicable product at the beginning of each treatment phase and have access to the Instructions for Use (IFU) to review. Participants will use the device assigned in treatment phase 1 overnight while sleeping for 4 weeks (28 days) before transitioning to the second assigned device in treatment phase 2. |
| | The primary endpoints will evaluate safety (skin injury) and efficacy (capture rate). Safety will be evaluated using the Draize Scale and efficacy will be measured based on daily capture rate. |
| | Nurses will visit daily to measure urine capture rate and to assess for skin irritation using the Draize Scale. |
| | The secondary outcomes include participative evaluation of the therapy and self-reported changes using questionnaires and preference surveys: Nocturia Quality of Life (N-QOL) assessment evaluated at baseline (previous treatment) and every 14 days through completion of each treatment phase (4 weeks/ 28 day period), PROMIS Sleep Disturbance measured at baseline and every 7 days through completion of each treatment phase, surveys (comfort & ease of use) completed by users at the end of each 4-week period, and end of study participant preference survey collected at study completion. |
| | Tolerability to be measured by number of days of actual use of both devices, and discontinuation rate attributed to the device's discomfort or inconvenience. |
| Investigational Device | Test product(s): |
| | PureWick[™] Female External Catheter (PWFX30) (U.S.) and (PWFX30E) (EU) |

| Protocol Title | A Comparative Crossover Study on the Safety, Efficacy, and Patient Quality of Life Comparing PureWick TM System with an Established Comparator Overnight in the Home Setting for Incontinence. | | | | | |
|----------------|---|--|--|--|--|--|
| | PureWick[™] Urine Collection System (PW100, PW200) (U.S.) and (PW200E) (EU) | | | | | |
| | For regulatory status, refer to Regulatory Status row below within this table. | | | | | |
| | Reference/Comparator product(s): | | | | | |
| | Marketed Device: Hollister® Female Urinary Pouch External Collection Device | | | | | |
| | Ancillary Product(s): | | | | | |
| | PureWick[™] replacement Kit (PWKIT03) (U.S.) and (PWKIT03E) (EU) Absorbent under-pads Medium/Large sealing plastic bags Medical Triangular Graduated Cylinders, 1000mL Weighing Scales Urine Collection Bags for Hollister FUP Urine Bag Holders Mesh underwear PPE (Gloves, Chux) Barrier Paste Wipes Micropore tape Hair trimmers/clippers | | | | | |

| Participants | Adult female participants currently using incontinence products at night (e.g., nocturnal enuresis, nocturia, mobility limitation) will be recruited for this study from the study site. | | | | | | |
|--------------|--|--|--|--|--|--|--|
| | To best mimic potential users of the PureWick TM System, participants ≥ 18 years of age will be enrolled. It is desired that at least 90% of participants are ≥ 65 years of age. This study will enroll approximately 30 participants. | | | | | | |
| | Inclusion Criteria | | | | | | |
| | In order to be eligible to participate in this study, an individual must meet all of the following criteria: | | | | | | |
| | Adult Female Participants ≥18 years of age at the time of signing the informed consent. Currently use diapers or equivalent at night for urine capture ("Change complet" (FR)) Willing to comply with all study procedures in this protocol. Provision of signed and dated informed consent form. | | | | | | |
| | Exclusion Criteria | | | | | | |
| | Participants are excluded from the study if any of the following criteria apply: | | | | | | |
| | Has frequent episodes of bowel incontinence without a fecal management system in place; or Has moderate to heavy menstruation and cannot use a tampon or menstrual cup; or | | | | | | |
| | Has Urinary tract, vaginal or other chronic infections, active genital herpes; or Has Urinary retention; or | | | | | | |
| | 5. Is agitated, combative, and/or uncooperative and may remove the external catheter or pouch; or | | | | | | |
| | 6. Has any wound, open lesion or irritation on the genitalia, perineum, or sacrum; or | | | | | | |
| | 7. Has any pre-existing neurological, psychiatric, or other condition that would confound quality of life assessment or would make it difficult to self-report on quality-of-life questionnaires in the opinion of the investigator; or | | | | | | |
| | 8. Is known to be pregnant at time of enrollment (for | | | | | | |

| Protocol Title | A Comparative Crossover Study on the Safety, Efficacy, and Patient Quality of Life Comparing PureWick TM System with an Established Comparator Overnight in the Home Setting for Incontinence. | | | | |
|------------------------------|--|--|--|--|--|
| | women of childbearing age); or 9. Any other condition that, in the opinion of the investigator, would preclude them from participating in the study. 10. Is under supervision of a legally authorized representative | | | | |
| Intervention(s)/Procedure(s) | The PI or designee/nurse defined by the Draize Skin Score will assess skin and determine readiness for each treatment phase. Participants assigned to both treatment arms will place and remove the FEC (female external catheter) or FUP (Female Urinary Pouch) after standardized teaching is completed on the first day of the treatment phase. Participants will use the device assigned in treatment phase 1 and 2 overnight while sleeping for 4 weeks (28 days). There will be a minimum washout period of 2 weeks (not to exceed 4 weeks) between treatment phases. | | | | |
| Investigational Sites | Approximately 2 sites in France and approximately 2 sites in the U.S. | | | | |
| Data Monitoring Committee | N/A | | | | |
| Regulatory Status | Post-Market, Non-significant risk PureWick[™] System Class I, non-sterile device, CE marked, currently marketed in Europe Class I, 510(k) exempt device currently marketed in the U.S. This investigation will use the PureWick[™] System for its intended purpose. | | | | |
| Trial Duration | Estimated start date: (First Patient In): 19 Sep 2023 Estimated end date (Final Clinical Study Report): October 2024 | | | | |

| Protocol Title | A Comparative Crossover Study on the Safety, Efficacy, and Patient Quality of Life Comparing PureWick TM System with an Established Comparator Overnight in the Home Setting for Incontinence. |
|------------------------------|--|
| Regulatory Agency Identifier | NCT05710718 (USA) |
| Number(s): | IDRCB: 2023-A01727-38 (France) |

CONFIDENTIAL

1.2 Schema

*NQOL, PROMIS, Preference & Ease of Use assessments and questionnaires. Will be administered for both treatment phase 1 and 2.

**Study Preference interview will only occur after participants have completed the study.

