| Participants wear investigational device | | Х | Х | Х | Х | | | | Х | Х | Х | Х | | |
| Nurses Measure Urine Output | | | Х | Х | Х | Х | | | | Х | Х | Х | Х | |
| Nurses Post-Weigh Overnight Pads and Mesh Underwear (if applicable) | | | Х | Х | Х | Х | | | | Х | Х | Х | Х | |
| Participant Completes Preference Survey | | | | | | X* | | | | | | | X* | |

CONFIDENTIAL

| | | | Daily Study Home Visits | | | | | | | | | | | |
|---|---------------------------|---------------------------|-------------------------|---------------|---------------------|---------------|------------------|------------------------------------|--------------------------|--------------------|------------------|---------------------|------------------|------------------|
| Procedure | Screening / Enrollment | Ph 1 Baseline Day 1 | Ph1 Day 2-14 | Ph1 Day 15 | Ph1 Day 16-28 | Ph1 Day 29 | Ph1 Day 30 | Washout Day 29-42 (+14 days) | Ph2 Baseline Day 1 | Ph2 Day 2-14 | Ph2 Day 15 | Ph2 Day 16-28 | Ph2 Day 29 | Ph2 Day 30 |
| Participant Completes End of Study Preference Survey | | | | | | | | | | | | | X* | |
| AE review (If applicable) | | | | | | | | | | | | | | |
| SAE review (If applicable) | | | | | | | | | | | | | | |
| Device Deficiencies (If applicable) | | | | | | | | | | | | | | |

*To be completed per treatment schedule or upon treatment discontinuation, whichever comes first.

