4.4 End of Study Definition

A participant is considered to have completed the study after she has completed both treatment phases and all required questionnaires.

The end of the study is defined as the date of completion of the last participant in the study.

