7.4 User Preference Questionnaire

Prior to each treatment phase completion, the participant will be asked to complete a short questionnaire on their experience with the PureWickTM System or the Hollister® FUP. The questionnaire is designed to assess the following:

- Comfort with PureWick[™] FEC/PureWick[™] Urine Collection System or the Hollister[®] Female Urinary Pouch External Collection Device
- Ease of use in placing and removing the PureWickTM FEC and the Hollister[®] Female Urinary Pouch External Collection Device

After completing both treatment phases for the study, the participant will complete the preference questions on their experience with the PureWickTM System and the Hollister® FUP. The survey is designed to assess the following:

• The participants preferred device after using both the PureWick[™] FEC/PureWick[™] Urine Collection System and the Hollister® Female Urinary Pouch External Collection Device.

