Appendix 16: End of Study Participant Preference Survey (Sample)

| Participant Number: | | | | | |
|--|--|--|--|--|--|
| | | | | | |
| Thank you for participating in this study. Now that you have experienced the use of two urine collection devices, please answer a few questions about your experiences with the devices. | | | | | |
| As a reminder, during the study, you used two devices overnight while sleeping: | | | | | |
| During the first part of the study, you used the PureWick™ Urine Collection System/Hollister Female Urinary Pouch External Collection Device. | | | | | |
| During the second part of the study, you used th System/Hollister Female Urinary Pouch Extern | ne PureWick™ Urine Collection al Collection Device. | | | | |

1. Do you remember using each of these devices?

Yes No

<*If No or if there is significant difficulty in differentiating the 2 study phases, discontinue the interview.*>

2. Which device did you prefer?

PureWick[™] Urine Collection System

Hollister® Female Urinary Pouch External Collection Device

3. What made you choose the <PureWick/Hollister> device? Why did you prefer that device?

<*Ask follow-up questions, as much as practical, to better understand the participant's preference>*

- 4. Please think about how your skin felt when using each device. Which caused you to feel LESS skin irritation, the PureWick[™] device or Hollister[®] device?
 - PureWick[™] Urine Collection System
- Hollister® Female Urinary Pouch External Collection Device
- No difference
- _____ Do not recall

Why did you choose the PureWick/Hollister?

Thank you for taking the time to answer these questions!

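### The rules conflict on whether a woman who used both devices but stopped the second one early is asked the End of Study Preference Survey, so she can drop out of a secondary endpoint

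*Protocol*

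**What the plan says.** The protocol synopsis and section 3.0 list overall preference, from the end-of-study survey, as a secondary endpoint. Two kinds of rule govern who is asked.

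**Completers only.** Under the Schema (protocol 1.2), the "Study Preference interview will only occur after participants have completed the study". Protocol 4.4 counts a participant as complete "after she has completed both treatment phases and all required questionnaires". Protocol 7.4 agrees: "After completing both treatment phases for the study, the participant will complete the preference questions". SAP 2.1 places the final preference question after completion of both treatments.

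**Scheduled day or discontinuation.** In protocol 1.3 the row "Participant Completes End of Study Preference Survey" has a single starred mark, under Phase 2 Day 29. The star means: "To be completed per treatment schedule or upon treatment discontinuation, whichever comes first". SAP Table 2 repeats the star and footnote, with the mark apparently under Phase 2 Day 30.

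Three other passages bear on it:
- Protocol 7.2.14 step 6, a Day 29 step, gives the survey when that day is the last of Phase 2 treatment.
- Protocol 7.2.7 step 5 sends a woman with a Draize score of 4 out of the phase and into washout, so leaving a phase is not the same as leaving the study. N-QoL is the only questionnaire named at that stop.
- Protocol 8.1 allows no further assessments once a participant discontinues the study.

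**The concern.** The preference question needs experience of both devices. It does not need both 28-day phases to be finished. A woman who wore the first device for four weeks and gave up on the second after ten nights can say which she prefers, and her answer is likely to be a firm one. Under the completers-only wording she is not asked; under the star she is. Sites can follow either passage in good faith, so the set of respondents depends on which one they read.

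The loss is unlikely to be random. Women stop a device because it is uncomfortable or inconvenient (itself a secondary tolerability endpoint) or because of skin injury. If their answers are missing and stops fall mainly on one device, the preference result moves towards the device that was stopped.

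**Working it through.** The plan gives no preference rate, stopping rate or precision target for this item, so there is no figure to reproduce. The check is a comparison of the rules, followed by an illustration.

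**Step 1. Apply each rule to each type of woman.**

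| Woman | 1.2, 4.4, 7.4, SAP 2.1 | Star (1.3, SAP Table 2) | 7.2.14 step 6 | 8.1 |
|---|---|---|---|---|
| Finishes both phases | Asked | Asked | Asked | Not relevant |
| Uses both, stops Phase 2 early, stays in study | Not asked | Due at the stop | Silent (Day 29 step) | Not relevant |
| Uses both, stops Phase 2 early, leaves study | Not asked | Due at the stop | Silent | Bars it |
| Stops Phase 1 early, then reaches Phase 2 Day 29 | Unclear: has not plainly completed both phases | Due at Phase 2 Day 29 | Asked | Not relevant |

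Rows 2 and 3 are direct contradictions. Row 4 is an ambiguity. All these women have used both devices.

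**Step 2. Illustrate the size.** N = 30 is the planned enrolment; everything else is assumed. Let all 30 use both devices, let k stop the same device early and prefer the other, and let the remaining N − k split evenly. If L of the stoppers are not asked, the reported preference for the other device is

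((N − k)/2 + k − L) / (N − L).

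- k = 6, L = 0: (12 + 6)/30 = 60%.
- k = 6, L = 3: 15/27 = 55.6%.
- k = 6, L = 6: 12/24 = 50%.
- k = 4, L = 0, 2, 4: 17/30 = 56.7%, 15/28 = 53.6%, 13/26 = 50%.

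The middle case, half the stoppers lost, has a natural basis. With 1:1 sequence randomisation, about half of those who stop a given device would do so in Phase 1. They could still be asked at Phase 2 Day 29 under 7.2.14 step 6. All are lost only if sites also treat Phase 1 stoppers as non-completers.

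**Step 3. Bounds without assuming what the missing women prefer.** If x of n respondents prefer one device and m women are not asked, the proportion among all n + m lies between x/(n + m) and (x + m)/(n + m). With n + m = 30 and about 70% of respondents preferring one device:

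| Not asked | Reported | Range for all 30 |
|---|---|---|
| 3 | 19/27 = 70% | 63% to 73% |
| 6 | 17/24 = 71% | 57% to 77% |
| 9 | 15/21 = 71% | 50% to 80% |

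The range is as wide as the share not asked.

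**Step 4. Look for an analysis rule.** SAP 5.2.3.1 to 5.2.3.5 cover N-QoL, PROMIS, the two tolerability measures, and comfort and ease of use. None gives an analysis or denominator for the end-of-study preference item. The table shells, listed as SAP Appendix 1, are not in the text available and may address it.

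**The case against.** **The star already reaches the Phase 2 stopper.** This stands. Its mark is in a Phase 2 cell, so on the natural reading it makes the survey due when Phase 2 treatment is stopped. The star's effect should be kept and the completers-only text changed to match. It does not remove the conflict while 1.2, 4.4, 7.4 and 8.1 say otherwise.

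**Phase 1 stoppers are mostly covered.** This largely stands. Step 6 of 7.2.14 depends on the last day of Phase 2 treatment and does not ask whether Phase 1 was finished. What remains is the doubt over whether such a woman counts as having completed both phases.

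**The effect is small and conditional.** In the middle case the shift is about 3 to 4 points. The standard error of a proportion near 50% with 30 women is √(0.25/30), about 9 points, and no formal test is planned. Stops on both devices would partly cancel. Tolerability and comfort data also record rejection of a device. All of this limits the consequence, but none of it says who belongs in the preference denominator.

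**A stronger reading to avoid.** Because the footnote names no phase, a reader might infer that the survey falls due at the first device stop. A woman stopping Phase 1 would then be asked before using the second device, have the interview ended at question 1 of Appendix 16 ("Do you remember using each of these devices"), and never be asked again. The documents do not support this. The row has no Phase 1 mark, whereas N-QoL, PROMIS and the per-phase survey are starred separately in each phase. Step 6 of 7.2.14 ties this survey to the last day of Phase 2, and the form presumes that two devices were used. Step 6 would in any case require the survey again at the end of Phase 2. It is a possible misreading that clearer wording would prevent, not something the schedule directs.

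**Conclusion.** The point holds for women who used both devices and stopped the Phase 2 device early: the schedule makes the survey due and four other passages exclude them, with 8.1 adding a bar for those who leave the study. For women who stopped Phase 1 early and went on to Phase 2, the text is ambiguous, not contradictory.

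The size cannot be derived from the documents. With 6 of 30 women stopping the same device, the understatement is 4.4 points if half are lost (60% against 55.6%) and 10 points if all are (60% against 50%). The second figure is a worst case: every stopper stops the same device, prefers the other and goes unasked. The direction, towards the stopped device, also depends on stops being concentrated on one device. That the missingness is informative is a judgement from the likely reasons for stopping, not something the plan reports. This should be corrected because the endpoint's respondent set is undefined and the repair is cheap.

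**What to change.** 1. In protocol 1.2 and 7.4 and SAP 2.1, replace the completion condition with: given once, after the last use of the Phase 2 device (scheduled or early), to every woman who used both devices for at least one night, whether or not she finished either phase.
2. Keep the star on this row in protocol 1.3 and SAP Table 2, but state that it refers only to discontinuation of Phase 2 treatment.
3. Align 7.2.14 step 6 so that it also covers an early Phase 2 stop. Align 4.4, which is circular at present: the Schema puts the interview after completion, while completion requires all questionnaires. In 8.1, allow this one survey at a Phase 2 stop if the woman agrees.
4. Reconcile the survey day: Phase 2 Day 29 in the protocol schedule, apparently Day 30 in the SAP schedule.
5. In the SAP, report preference with this set as the denominator, and show early stoppers of each device separately.

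The cost is wording in two documents and a few extra short interviews. Some respondents will have had only brief experience of one device; the separate display makes that visible. No device use or treatment-stopping rule changes.
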